1. SYNOPSIS

Study Objective	To assess and compare tissue aggregation and visualization of two (2) Hyaluronic Acid fillers via ultrasound
Methodology	Randomized, split-face, subject-blinded, comparative study
Number of Subjects at the end	15 subjects to complete
Study duration	24 weeks
Test products	Restylane Contour Juvéderm Voluma
Conditions of use	Per on-label instruction
Study visits	Day 0, week 4, and week 24
Specific Inclusion Criteria:	
 ○ Demographics and study skin conditions - Any race and ethnicity (to be recorded) - Fitzpatrick skin type (to be recorded) - Women or men - Age: 22 to 65 years old - Subject with midface volume loss and contour deficiency ○ Administrative - Ability of giving consent for participation in the study - Agreement to adhere to the procedures and requirements of the study and to report to the institute on the day(s) and at the time(s) scheduled for the assessments.
Specific Exclusion Criteria:	
 ○ Skin conditions - History of allergy or hypersensitivity to lidocaine and/or injectable hyaluronic acid (HA) - Previous permanent or semi-permanent implant in proposed treatment area - Previous biodegradable tissue augmentation therapy in the proposed treatment area within 12 months prior to the baseline visit

Protocol Version 2:

This document contains confidential, proprietary information.

	
 - History of other facial treatment/procedure at the study area (midface) in the previous 6 months that would potentially interfere with study injections (e.g., facial surgery, oral surgery, resurfacing, mesotherapy, lipolytic injections, botulinum toxin injections)

Procedure
	
 ○ D0 
 - Subjects will report to the site as D0 visit, will be given an informed consent form, HIPAA form, photography release form, Code of Conduct form, and medical history form to complete. - Subjects will be screened on the basis of the selection criteria for study qualification. - Ultrasound will be performed on enrolled subject's cheeks, left and right side will be assessed separately. - 2D photography will be performed at neutral expression (3/4 left, front, 3/4 right) and at smiling (3/4 left, front 3/4 right). 3D photography will be performed at neutral expression on entire face. - Investigator will perform injection to the subjects, based on the predetermined randomization and the test products' instruction to achieve the maximum correction. - Immediately post-injection, ultrasound will be performed at the same location of the injection, on either side of the face. ○ W4 
 - Subjects to return to the site at week 4 post-treatment (± 3 days). - Ultrasound, 2D and 3D photography will be performed similarly to D0. - Self-assessment questionnaire will be performed by the subjects. - If needed, subjects will be offered a touch up to correct uneven side upon study completion. ○ W24 
 - Subjects to return to the site at week 24 post-treatment (± 3 days). - Ultrasound, 2D and 3D photography will be performed similarly to D0. - Self-assessment questionnaire will be performed by the subjects.

Statistical analysis
	
Comparison of filler aggregation, volume change, and self-assessment questionnaire.

3. LIST OF ABBREVIATIONS AND DEFINITIONS OF TERMS

AE	Adverse Event
°C	Degrees Celsius
CRF	Case Report Form
etc.	et cetera
e.g.	for example (Latin; exempla gratia)
°F	Degrees Fahrenheit
GCP	Good Clinical Practice
HA	Hyaluronic Acid
HIPAA	Health Insurance Portability and Accountability Act of 1996
ICH	International Conference on Harmonization
ICT	Information and communication technologies
i.e.	that is (Latin; id est)
IEC	Independent Ethics Committee
IRB	Institutional Review Board
N or n	Number
%	percent
SAE	Serious Adverse Event
SD	Standard deviation
SOP	Standard Operating Procedure

4. BACKGROUND AND RATIONALE

The hallmark signs of aging in the mid-face are often characterized by the decrease in skin elasticity and thickness, loss of tissue volume and body mass, and redistribution of fat tissues. Overtime, they result in the formation of deep wrinkles, folds, sagging skin, and hollowing.¹ One of the most popular non-invasive aesthetic treatments for mid-face volume restoration is the use of hyaluronic acid (HA) fillers. Due to their safety, effectiveness, and reversibility by hyaluronidase, HA fillers can help correct facial wrinkles and folds, while improving facial contour and volume augmentation.¹⁻³

Currently in the market, there are various types of HA fillers have been approved for the midface volume restoration. Among them are two well-known fillers: Restylane® Contour (Galderma, Uppsala, Sweden) and Juvéderm® Voluma® (AbbVie/Allergan Aesthetics, Irvine, CA). They each contain 20mg/mL of hyaluronic acid with different crosslinking gel technologies, resulting in varying biophysical properties. Restylane® Contour has moderate lifting capacity (G') and flexibility whereas Juvéderm® Voluma® has a higher lifting capacity (G') and low flexibility.

The mechanism that each HA filler integrates into the skin tissue reflects the overall appearance of the midface. This study is to investigate how the two HA fillers behave in the skin tissue using ultrasound.

5. STUDY OBJECTIVE AND CLINICAL HYPOTHESIS

5.1 Study Objective

To assess and compare tissue aggregation and visualization of two Hyaluronic Acid fillers via ultrasound.

5.2 Clinical Hypothesis

When each HA filler is injected and integrated into the tissue, it will add volume to the skin to achieve different lifting and contouring effect.

6. SELECTION AND DISPOSITION OF STUDY POPULATION

6.1 Number of Subjects

A minimum 15 subjects meeting inclusion/exclusion criteria listed below will be enrolled on the study to achieve 15 subjects who complete the study as planned.

6.2 Study Population Characteristics

Males and females of any skin type with diagnosis of midface volume loss and contour deficiency.

6.3 Inclusion Criteria

1. Subjects of 22 to 65 years of age.
2. Subjects with a clinical diagnosis of midface volume loss and contour deficiency, and in the opinion of the investigator, is otherwise a good candidate for treatment with HA fillers.
3. Subjects of any gender.
4. Subjects of any race and ethnicity.

Protocol Version 2:

This document contains confidential, proprietary information.

Protocol GLI.04.US.SL.015

CONFIDENTIAL

5. Subjects of any Fitzpatrick skin type.
6. Subjects who are able and willing to provide written informed consent prior to any study related procedures.
7. Subjects who agree to be photographed at each visit.
8. Subjects apprised of the Health Insurance Portability and Accountability Act of 1996 (HIPAA) and applicable state Bill of Rights.
9. Subjects who agree to adhere to the procedures and requirements of the study, to report to the institute on the day(s) and at the time(s) scheduled for the assessments, and to complete all required visits.

6.4 Exclusion Criteria

1. Subjects with any diseases, condition or presentation that may, in the opinion of the investigator, may put the subject at risk, may confound study results, or may interfere with participation in the study.
2. Subjects who are pregnant or breast-feeding, or who plan to become pregnant or breast feed during the course of the trial.
3. Subjects that are relatives of the investigator or are themselves or a relative of any study staff or any Galderma employee.
4. Subjects who have participated in an investigational study within 30 days of enrollment; participated in biologic investigational studies within 90 days of enrollment, or subjects planning to participate in any other interventional clinical research study while enrolled in this trial.
5. Subjects with history of allergy or hypersensitivity to lidocaine and/or injectable HA
6. Subjects with previous permanent or semi-permanent implant in proposed treatment area
7. Subjects with previous biodegradable tissue augmentation therapy in the proposed treatment area within 12 months prior to the baseline visit
8. Subjects with history of other facial treatment/procedure at the study area (midface) in the previous 6 months that would potentially interfere with study injections (e.g., facial surgery, oral surgery, resurfacing, mesotherapy, lipolytic injections, botulinum toxin injections).
9. Use of concomitant medications that have the potential to prolong bleeding times such as anticoagulants or inhibitors of platelet aggregation (e.g., aspirin or other nonsteroidal anti-inflammatory drugs, Omega 3 or Vitamin E), within 14 days prior to injection. Omega 3 and Vitamin E were acceptable only as part of a standard multivitamin formulation.

6.5 Concomitant Therapies

All treatments and therapies used 30 days prior to enrollment (visit 1/baseline) or 90 days prior to enrollment for biologics and all treatments or therapies used during the course of the study must be recorded in the Case Report Form (CRF) or electronic Case Report Form (eCRF).

6.5.1. Authorized Therapies

Unless listed under the exclusion criteria (Section 6.4) or in Prohibited Therapies (Section 6.5.2), other therapies to treat ongoing conditions are authorized.

6.5.2. Prohibited Therapies

None other than as specified in the Inclusion/Exclusion criteria.

Protocol Version 2:

This document contains confidential, proprietary information.

Protocol GLI.04.US.SL.015

CONFIDENTIAL

The decision to administer a prohibited medication/treatment should be made with the safety of the subject being the primary consideration. Whenever possible, Galderma Laboratories, L.P. should be notified before the prohibited medication/treatment is administered to discuss possible alternatives.

If a subject receives prohibited therapy during the study, the subject may be allowed (at the discretion of the investigator / Galderma Laboratories, L.P.) to continue in the study for safety evaluation purposes, only.

7. STUDY TREATMENT

The term “study treatment” refers to the study products (HA Fillers, see Section 7.1)

7.1 Product Identification and Use

Study product: Restylane® Contour	
Form	Transparent gel of HA with the addition of lidocaine hydrochloride 3 mg/mL
Mode of Administration	Injection
How supplied	Pre-filled plastic syringes containing 1 mL of gel. Each syringe is co-packed with two ultra-thin wall needles.
Lot numbers	19741
Storage and Handling	The syringes are to be stored in the original packaging, under controlled room temperature conditions 20°C to 25°C (68°F to 77°F), protected from freezing and sunlight.

Study product: Juvéderm® Voluma®	
Form	Sterile, biodegradable, non-pyrogenic, viscoelastic, clear, colorless, homogenous gel implant of HA crosslinked with BDDE, formulated to a concentration of 20 mg/mL and 0.3% w/w lidocaine in a physiologic buffer.
Mode of Administration	Injection
How supplied	Individual treatment syringes with needles.
Lot numbers	VB20B20024
Storage and Handling	Store at room temperature (up to 25°C/77°F). DO NOT FREEZE.

7.2 Additional Products and Materials

The Sponsor will only provide Restylane® Contour for the study. The study overhead will cover any additional materials or supplies.

Protocol Version 2:

This document contains confidential, proprietary information.

Protocol GLI.04.US.SL.015

CONFIDENTIAL

7.3 Study Product Accountability

Upon receipt of the study products, the investigator or designee will conduct an inventory. In accordance with federal regulations, the investigator must agree to keep all test article in a secure location with restricted access. Designated study personnel will provide the test article to the subjects in accordance with the protocol.

During the study, the investigator must maintain records of study treatment dispensation and collection for each subject. This record must be made available to the study monitor for the purposes of verifying the accounting of clinical supplies. Any discrepancies and/or deficiencies between the observed disposition and the written account must be recorded along with an explanation. At the conclusion of the study, the investigator will be responsible for returning all unused study product (i.e., Restylane® Contour) unless otherwise instructed by the Sponsor. Shipping label and cost will be provided to the investigator by the Sponsor.

7.4 Method of Treatment Assignment

Before the start of the study, a randomization list will be prepared by the Sponsor utilizing a computer-generated software.

7.5 Treatments Administered

The study products contain lidocaine hydrochloride, but additional topical or local anesthesia or ice pack may be used at the discretion of the Investigator to enhance the experience of the subjects. Any additional topical or local anesthesia used will be recorded in the CRFs.

The injection tools (needles or cannulas) will be determined at the discretion of the Investigator. However, for each subject, the Investigator must use the same type of injection tool to perform injection for both sides of the face. Switching device within the subject will not be allowed in order to avoid any inconsistent comparison. Either needles or cannulas will be used per subject. The brand name, gauge and length of the cannulas and incision needles used by the Investigator will be recorded in the CRFs.

The study products will be injected into the midface at the supraperiosteal to subcutaneous layer in the prezygomatic space lateral to the plane of the medial canthus, along the plane of the zygomatic arch ~1cm medial to hairline (described in Figure 1 below).

Protocol Version 2:

This document contains confidential, proprietary information.

[figure not shown]

Figure 1. Description of injection boundary.

The amount of each study products needed varies between subjects and within subjects bilaterally, given the natural asymmetry of the face. However, subjects will be treated to optimal correction of the midface as agreed by the Investigator and subjects. The product volume injected during each treatment session for each subject will be recorded in the CRFs.

8. STUDY PROCEDURES

There will be three (3) visits during the course of the study:

1. Visit 1 – Screening/Baseline/Day 0
2. Visit 2 – Week 4 (Day 28)
3. Visit 3 – Week 24 (Day 168)

Test design / flow chart	D0	W4	W24
Informed consent	X		
Photo consent	X		
Demographics/Med History	X		
Concomitant Meds.	X		
Inclusion and exclusion criteria	X		
Randomization	X		
Case report form (CRF)	X	X	X
Injection per on-label instruction	X		
Touch up (if applicable)		X	
Ultrasound	X*	X	X

Protocol Version 2:

This document contains confidential, proprietary information.

Protocol GLI.04.US.SL.015

CONFIDENTIAL

Standardized photography (2D and 3D)	X	X	X
Self-assessment questionnaire		X	X
AE Reporting	X	X	X

*Ultrasound at D0 will be performed before injection and immediately post-injection for each product.

8.1 Visits and Examinations

8.1.1. Screening/Baseline/Day 0 Visit (Visit 1)

1. Subjects will report to the testing clinical at D0 for baseline screening.
2. Prior to beginning of any study related activities, subjects will be informed about the purpose and nature of the study, the expected post-treatment events, and the potential risks involved with the treatments.
3. Subjects will be given an informed consent form, HIPAA form, photography release form, and Code of Conduct form to read.
4. Once subjects have completed reading, they will be interviewed to ensure their understanding of the aforementioned forms and be given the opportunity to ask any study related questions.
5. Subjects who agree to sign the aforementioned forms will be asked to complete a demographic information, medical history form, and concomitant medication form. Subjects declining to sign any of the forms will be dismissed from the study.
6. Subjects will be screened and qualified on the basis of the subject inclusion and exclusion criteria. Subjects failing to meet criteria will be dismissed from the study.
7. Subjects will have the below assessments by Investigator or a trained Clinic staff:
 - a. Clinical 2D photography by VISIA at neutral expression (3/4 left, front, 3/4 right), at closed-mouth smile (3/4 left, front, 3/4 right), and at open-mouth maximum smiling (3/4 left, front 3/4 right)
 - b. Clinical 3D photography by Vectra at neutral expression of full face
 - c. Ultrasound on each cheek at neutral expression and at maximum smiling (left and right). Note: ultrasound assessment will be performed at the same area of the injection.
8. Clinic staff or Investigator will assign the appropriate test treatment to each side of the face based on the predetermined computer-generated randomization.
9. Investigator will instruct the subjects on each treatment administration procedure and perform the treatments.
10. Investigator or Clinic staff will record the details of the administration, amount of each treatment used for each cheek and any subsequent adverse events (AEs) in the CRF.
11. Immediately post-injection, subjects will have the below assessment by Investigator:
 - a. Ultrasound on each cheek at neutral expression and at maximum smiling (left and right). Note: ultrasound assessment will be performed at the same area of the injection.
12. Subjects will be instructed on any standard care post-treatment and when to contact the Investigator in case of emerging AEs.
13. Subjects will be scheduled for a follow-up visit at Week 4 or Day 28 (± 3 days) and dismissed from the Clinic.

Note: Subject screening /baseline/Day 0 must be on the same day.

Protocol Version 2:

This document contains confidential, proprietary information.

Protocol GLI.04.US.SL.015

CONFIDENTIAL

Note: Whenever possible, the same investigator/staff that perform the baseline assessments and treatments should perform these assessments for each individual subject for the entire duration of the study. In the event of a change in the assigned investigator/staff for a given subject, the reason for change must be documented.

8.1.2. Visit 2 (Week 4 or Day 28 \pm 3 days)

1. Clinic staff or Investigator will record any AEs that are observed or reported.
2. Subjects will have the below assessments:
 - a. Clinical 2D photography by VISIA at neutral expression (3/4 left, front, 3/4 right), at closed-mouth smile (3/4 left, front, 3/4 right), and at open-mouth maximum smiling (3/4 left, front 3/4 right)
 - b. Clinical 3D photography by Vectra at neutral expression of full face
 - c. Ultrasound on each cheek at neutral expression and at maximum smiling (left and right). Note: ultrasound assessment will be performed at the same area from Visit 1.
 - d. Self-assessment questionnaire
3. Investigator will assess and offer the subjects an optional touch-up on the cheeks to reach the optimal aesthetic result.
4. If touch-up is needed, the same study treatment and type of injection tool used for each side of the face for the baseline treatment need to be used for this step. Investigator or Clinic staff will record the amount of the treatment used for the assigned cheek in the CRFs.
 - a. Touch-up treatment was not to be performed if the subjects have a disease or condition described in the exclusion criteria, or an ongoing treatment-related AE that in the opinion of the Investigator would be worsened by a touch-up treatment.
5. Once completed, subjects will be scheduled for a follow-up visit at Week 24 or Day 168 (\pm 3 days) and be dismissed from the Clinic.

8.1.3. Visit 3 (Week 24 or Day 168 \pm 3 days)

1. Clinic staff or Investigator will record any AEs that are observed or reported.
2. Subjects will have the below assessments:
 - a. Clinical 2D photography by VISIA at neutral expression (3/4 left, front, 3/4 right), at closed-mouth smile (3/4 left, front, 3/4 right), and at open-mouth maximum smiling (3/4 left, front 3/4 right)
 - b. Clinical 3D photography by Vectra at neutral expression of full face
 - c. Ultrasound on each cheek at neutral expression and at maximum smiling (left and right). Note: ultrasound assessment will be performed at the same area from Visit 1.
 - d. Self-assessment questionnaire
3. Once completed, subjects will be dismissed from the Clinic.

8.2 Discontinued Subjects

Any subject is free to discontinue his/her participation in this study at any time and for whatever reason, specified or unspecified, and without prejudice.

Protocol Version 2:

This document contains confidential, proprietary information.

Protocol GLI.04.US.SL.015

CONFIDENTIAL

An investigator may decide to discontinue a subject from the study for safety reasons or when it is in the best interest of the subject. Galderma Laboratories, L.P. may also decide to prematurely terminate or suspend the study or the participation of a subject in the study. All data gathered on the subject prior to termination should be made available to Galderma Laboratories, L.P.

Criteria for the discontinuation of a subject during the study will include the following:

- Adverse Event
- Lack of Efficacy
- Pregnancy
- Subject Request
- Protocol Violation
- Lost to Follow-up
- Any unmanageable factor, in the Investigator's opinion, that may significantly interfere with the protocol or interpretation of results.

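### Section 8.2 lets subjects be taken out of the study for lack of efficacy or a protocol violation when no product is left to stop, and Section 10 then drops all their data

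*Combined protocol and SAP*

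**What the plan says.** Section 8.2 states: "An investigator may decide to discontinue a subject from the study for safety reasons or when it is in the best interest of the subject". It also lets the sponsor end a subject's participation and gives no criterion for doing so. It then continues: "Criteria for the discontinuation of a subject during the study will include the following". Among the entries are "Lack of Efficacy", "Protocol Violation" and "Any unmanageable factor, in the Investigator's opinion, that may significantly interfere with the protocol or interpretation of results". None of these is tied to a measure, threshold, cheek or visit. On data, the section says only that what was gathered before termination goes to the sponsor. It mentions no exit assessment, and no option to stop product while staying in follow-up.

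Other sections bear on this:

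- **Treatment schedule.** The Section 8 flow chart marks injection at Day 0 only. Section 8.1.2 adds one optional touch-up at week 4. Week 24 (Section 8.1.3) consists of photography, ultrasound, a questionnaire and adverse event recording.
- **Analysis set.** Section 10 restricts all statistical analyses to completing subjects.
- **Enrolment.** Section 6.1 says a minimum of 15 "will be enrolled on the study to achieve 15 subjects who complete the study as planned".
- **Prohibited therapy.** Section 6.5.2 lets a subject who received it remain, for safety evaluation only.
- **Blinding.** The synopsis describes the study as subject-blinded. The investigator injects according to the allocation (Section 8.1.1), and the sponsor prepares the randomization list (Section 7.4) and receives the images (Section 9).

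**The concern.** Discontinuation criteria of this kind make sense where dosing is repeated and can be stopped. Here nothing is scheduled after the optional touch-up, so leaving the study protects no one from further product and costs the week 24 assessment, the only late outcome. Lack of efficacy is itself an outcome, and an interpretation concern can be prompted by one. A rule that permits exit on such grounds permits loss that depends on the result.

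The design and analysis make the loss larger than one missed visit. In a split-face study, one poor cheek takes the other cheek with it. Under the completers-only rule, data already collected at Day 0 and week 4 go too. Further enrolment brings the count back to 15 but does not bring back the lost outcomes. People who can know the side allocation are able to make the decision.

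**Working it through.** **The plan's own figure.** The 15 completers cannot be reproduced. The documents state no alpha, power, effect size, SD or dropout rate, and the minimum enrolled equals the number to complete. Every size below is therefore an illustration on assumed inputs.

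**Step 1: what a removal after week 4 costs.** Section 8.2 takes the subject out of the study, so there is no week 24 visit. Section 10 excludes non-completers from all analyses, so the Day 0 and week 4 values are lost as well. Section 6.1 allows another subject to be enrolled.

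**Step 2: how likely any loss is.** For a per-subject loss p, the chance of losing at least one of 15 is 1 - (1 - p)^15. This is 54%, 79% and 96% at p = 5%, 10% and 20%. To finish with 15, enrol 15/(1 - p) rounded up: 16, 17 and 19.

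**Step 3: bias in SD units.** Assumptions: normal week 24 changes, SD 1 per cheek, between-cheek correlation 0.3 to 0.7, products truly equal, 1,000,000 simulated pairs, and the worst 1, 2 or 3 of every 15 removed on the week 24 value.

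| Removed | Ranked on the poorer cheek: overstatement of each product's mean | Ranked on one product's cheek only: bias in the difference, favouring that product |
|---|---|---|
| 1 of 15 | 0.10-0.12 SD | 0.04-0.10 SD |
| 2 of 15 | 0.18-0.22 SD | 0.07-0.17 SD |
| 3 of 15 | 0.25-0.31 SD | 0.11-0.24 SD |

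In the middle column the between-product difference is unbiased. Because selection here acts on the week 24 value, the table shows the direction and an upper size.

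**Step 4: exit decided at week 4, the last scheduled look before week 24.** Assumptions: week 24 means 1.0 and 0.7 mL; SD 0.5 mL per cheek at both visits; between-cheek correlation 0.3 to 0.7; week 4 to week 24 correlation 0.3 to 0.7; correlation across both cheek and visit equal to the product of the two; touch-up ignored. A subject leaves if either cheek is below 0.2 mL at week 4.

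- *Equal week 4 means of 1.0 mL.* The chance for one cheek is Φ((0.2 - 1.0)/0.5) = Φ(-1.6) = 0.055, so at most 0.110 for either. With the correlations, 9-10% leave. The weaker filler's week 24 mean becomes 0.72-0.75 mL, and the difference stays 0.30 mL.
- *Week 4 means already 1.0 and 0.7 mL.* The weaker cheek's chance is Φ((0.2 - 0.7)/0.5) = Φ(-1.0) = 0.159, so at most 0.055 + 0.159 = 0.214 for either. With the correlations, 17-20% leave. The weaker filler's mean becomes 0.74-0.81 mL, and the difference becomes 0.26-0.29 mL.

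Of 15 subjects, 9-20% is about 1 to 3 (0.09 × 15 = 1.35; 0.20 × 15 = 3).

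**Step 5: with follow-up kept.** If every treated subject has the week 24 assessment and is analysed, bias from removal for a poor result is zero by construction.

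**The case against.** The strongest reply is that the list in Section 8.2 works partly as a list of reasons. It includes subject request and loss to follow-up, which nobody decides, and Section 11.5 speaks of recording a reason for discontinuation on the exit form. The investigator and the sponsor may discontinue a subject and are not obliged to. Section 6.5.2 shows that at least one kind of deviation need not end participation. All of this stands: the loss is permitted, not certain. The list is still worded as criteria for discontinuation, and no passage keeps such a subject in follow-up.

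Three stronger readings are tempting, and the documents do not support them.

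- **Exit on the week 24 result itself.** With the same assumed means and SD, dropping anyone below 0.2 mL at week 24 would lose 18-20%, shrink the difference to 0.24-0.27 mL and lift the weaker filler's mean to about 0.85 mL. No visit falls between week 4 and week 24, so that value is unknown until the visit that measures it. At week 4, the protocol's response to a poor result is an offered touch-up.
- **A difference always pulled toward zero.** If the products are equal at the time of exit and removal ignores side, the difference is unbiased. If removal follows one product's side, it favours that product.
- **Anything that touches interpretation forces removal, and so does a late visit such as Day 172.** The clause is limited to unmanageable factors and significant interference. A subject seen on Day 172 attends and can be imaged, so that is a visit-window question. A protocol violation also need not depend on outcome.

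A subject who withdraws because of dissatisfaction cannot be kept by any wording. The study is also small, and the assumed loss rates have no basis in the documents.

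**Conclusion.** The point holds in a limited form. Section 8.2 permits exit for reasons tied to outcome when no product remains to be stopped, and Sections 10 and 6.1 turn each such exit into the loss of a whole subject who may be replaced by one who stays. Each product's change from baseline would then tend to be overstated. The between-product difference is biased only if removal depends on which side did poorly, or if the products already differ when exit is decided; its direction is not fixed.

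On the assumptions of Step 4, the weaker filler's mean is overstated by 0.02-0.11 mL on a true 0.70 mL, and the 0.30 mL difference moves by at most about 0.04 mL. These sizes depend wholly on assumed means, SD, correlations and exit threshold. Withdrawal for safety, in the subject's best interest, on request or for pregnancy is not questioned. This is a cheap improvement, not a flaw that undermines the study.

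**What to change.** 1. In Section 8.2, separate the end of study product from the end of data collection. State that lack of efficacy, a protocol violation or an interpretation concern does not by itself end follow-up, and that every treated subject who still consents is asked to attend the scheduled week 24 assessment.
2. In Section 10, include the available data of all treated subjects, and keep completers as a supportive analysis. Without this, week 24 or other data retained under item 1 could still be excluded.
3. Record the reason for any exit before that subject's week 24 images are viewed, and report the reasons.
4. Leave the safety, best-interest, subject-request and pregnancy provisions (Sections 8.2 and 11.5) as they are.
5. Reconcile Section 6.5.2, where a subject given prohibited therapy may continue for safety evaluation only, with the protocol violation entry in Section 8.2.

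The cost is wording in Sections 8.2 and 10 plus the reconciliation in item 5, with no added visit. The small downside is that some week 24 data will come from subjects with deviations, which can be flagged in listings.
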